All suspected VTE and bleeding endpoints as well as hepatic abnormalities identified by the Investigator will be adjudicated by the CEC. Adjudication packages will contain copies of images (or films) of appropriate diagnostic tests, clinic notes, laboratory tests, discharge summaries, autopsy reports, etc. used in the subject work-up following a suspected event.

Investigators will maintain a confidential subject identification code list of names of all subjects randomized to study to allow the Investigator to reveal the identity of any subject when necessary.

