6.3.3.2. Month 2 (Visit 4) Procedures

- Record concomitant medications
- Count unused study drug tablets/ bottles/syringe and calculate compliance
- Dispense study drug medication and review dosing instructions
- Perform physical examination (see Section 9.10)
- Record vital signs (Section 9.9)
- Safety review for AEs/SAEs

- Review for endpoint events (VTE, bleeding)
 - The follow-up imaging performed if needed, must be always performed with the same modality as the initial diagnostic study

6.3.4. End of Main Treatment Period Visit (Month 3 or at least 6-12 weeks for Cohort 5, Visit 5) Procedures

All randomized subjects including those that have discontinued treatment will have an EOT assessment at Month 3 (within a ± 5 -day window).

The following will be performed at this visit:

- Perform physical examination (see Section [9.10](#))
- Vital signs (Section [9.9](#))
- Review concomitant medications
- Count unused study drug tablets/ bottles/syringe and calculate compliance
- Safety review for AEs/SAEs
- Review for endpoint events (VTE, bleeding)
 - Radiologic examination using the same diagnostic technique used at baseline to determine the thrombotic burden (see Section [7.1](#)).
 - VTE Radiologic Imaging (see Section [7.1](#)).
- Take samples for the following:
 - Liver function tests [ALT, AST, TBL, and ALP]
 - Serum creatinine
 - Hematology
 - Urine pregnancy test
- Dispense study drug medication and review dosing instructions per subject/parent's request and at the Investigator's decision to extend study treatment. After Month 3, the distribution of edoxaban or SOC may be for a 3-month period to align with the visit schedule, with the Sponsor's approval.

6.4. Extension Period (beyond Month 3 - Month 6, 9 and 12; Visits 6, 7, 8)

Per subject/parent's request and at the Investigator's decision, study treatment can be extended up to 12 months. At any time during the extended period, a subject can discontinue treatment and the study. In such a case a discontinuation study visit will be performed with a subsequent 30-day safety Follow-Up Visit (see [Table 17.1](#)).

The subjects on extended treatment will be followed for safety and efficacy assessment including bleeding events, recurrent VTE, and any treatment-related AEs at visit for Months 6 (Visit 6), 9 (Visit 7), and 12/ Discontinuation (Visit 8). Additionally, the subject will have a Follow-Up Visit (Visit 9) for safety assessment 30 days after treatment cessation. At Month

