7. EFFICACY ASSESSMENTS

7.1. Primary Efficacy Endpoint(s)

The primary efficacy endpoint is the composite endpoint consisting of incidence of symptomatic recurrent venous thromboembolic disease, death as result of VTE, and no change or extension of thrombotic burden (defined below) during the first 3-month period (for Cohort 5, the intended duration of treatment is 6-12 weeks).

All efficacy endpoints described below will be adjudicated in a blinded manner by the clinical events committee.

Radiologic examination

- Utilizing the same diagnostic technique at baseline and follow-up to determine the thrombotic burden.

Diagnosis of new/recurrent PE requires meeting 1 or more of the following criteria:

- A (new) intraluminal filling defect in segmental or more proximal branches of the pulmonary artery on spiral CT scan;
- A mismatched defect on a nuclear ventilation/perfusion (V/Q) scan compared to the prior imaging;
- A non-diagnostic lung scan accompanied by documentation of new deep vein thrombosis by (Doppler) ultrasonography or venography.

Diagnosis of symptomatic recurrent VTE requires the confirmation by appropriate diagnostic imaging (see imaging criteria of recurrent VTE) and at least one of the symptoms of VTE in the following table:

- Symptoms of VTE:

Locations	Symptoms
VTE in Upper limb (CVL or non-CVL related)	
• Collateral dilated vein on the chest• Superior vena cava syndrome• Chylothorax• Pain and/or Swelling in index limb• Reddish or purple discoloration
VTE in Lower extremity (CVL or non-CVL related)	
• Reddish or purple discoloration• Swelling• Pain

Catheter-related thrombosis	
 • Dysfunction of catheter (inability to aspirate blood) not attributed to catheter kinking • Catheter-sepsis • Thrombocytopenia (especially neonates)
Pulmonary embolism	
 • Dyspnea • Pain thorax-pleuritic chest pain • Hypoxemia-low O₂ saturation • Hemoptysis • Cough • Tachycardia • Tachypnea, • Fever • Syncope • Right heart failure • Cardiopulmonary arrest

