	
• Spiral CT pulmonary angiography (CTPA)• Magnetic resonance pulmonary angiography (MRPA) 
Alternative imaging techniques:
 
• Cardiac angiography• Conventional pulmonary angiography• echocardiography
Sinovenous thrombosis	
• Brain MRI, including T2 imaging and MRI with venography (MRV)• Pre and post-contrast CT scan with venography (CTV) 
Alternative imaging techniques:
 
• Doppler flow US; if fontanelle open
Renal Vein thrombosis	
• US
Splanchnic and hepatic veins and vena cava	
• Doppler/US• CT/Scan

In certain cases, the use of 2 techniques may be required to objectively confirm the diagnosis of recurrent VTE. Further recommendations will be provided in the imaging manual but will be left for Investigator's discretion.

Diagnosis of fatal VTE is based on 1 or more of the following:

- Objective diagnostic testing
- Autopsy
- Death which cannot be attributed to a documented cause and for which VTE cannot be ruled out.

Thrombotic burden will be assessed by comparison of the diagnostic method used at baseline and at Month 3 \pm 5 days (for Cohort 5, at 6 to 12 weeks \pm 5 days) in the absence of symptomatic recurrent VTE. Hence, the same imaging technique that is used at the enrollment of the subject into the study will be required to be used at the end of the observational period \pm 3 days. A thrombotic burden endpoint will be registered if there is no regression of the thrombus size or extension of the thrombus at Month 3 visit \pm 3 days (for Cohort 5, at 6 to 12 weeks \pm 3 days) after randomization.

Additionally, thrombotic burden will be assessed at Month 12 \pm 5 days / Discontinuation Visit, for those subjects who participate in the Extension Period.

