**Samples taken as part of routine care outside the study requirements may be analyzed by local laboratories and the results used to qualify the subject provided the tests were performed for the newly diagnosed index VTE before randomization. If central laboratory is also used at the same visit with a resulting discrepancy for exclusion criteria, the local laboratory result will still be used to qualify the subject.

^a Randomization may occur in IXRS the day prior to dosing for clinical logistics.

^b Follow-Up Visit will be performed 1 month after the subject completes the study (6 weeks - Month 3 or Month 12 or 30 days after discontinuation from study in the extension period).

^c Scheduling of visits within windows should be done with caution to the drug supply available in a dispensing unit. PK/PD assessment on Day 5 cannot be performed before Day 5.

^d Targeted physical examination performed by an Investigator or other healthcare professional designated by the Investigator.

^e Vital signs include heart rate, body temperature, and sitting or supine blood pressure (Section 9.9).

^f INR assessment for adjustment of VKA dosages will be performed every month as per SOC. Additional interim evaluations may be performed at the discretion of the Investigator. INR will be assessed at Screening/Qualification visit if prior VKA was given or to be taken.

^g Investigator discretionary assessment of anti-FXa to be performed to determine if SP or LMWH are at therapeutic levels.

^h If image was taken for recurrent VTE after Month 3 but before discontinuation, then no image is needed at Month 12/Discontinuation. Optional Month 3 imaging can be done if recurrent VTE occurs prior to Month 3.

ⁱ Highly sensitive urine pregnancy test to be performed for females of childbearing potential.

^j AE/SAE reporting should occur throughout the study and not be restricted to specific visits.

^k Endpoint events should be reported as soon as site personnel learn of the event. Endpoint event should occur throughout the study and not be restricted to specific visits.

^l Prior medications includes 30 days prior to Screening/Qualification visit.

^m There is no dispensing or drug accountability requirement for Visit 2a for edoxaban arm for those subjects enrolled in the PK/PD evaluation because drug is expected to be dispensed on a monthly basis. The subject will need to bring in his/her edoxaban therapy for a single dosing treatment.

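### Table 17.1 footnote h makes the Month 3 scan optional after any recurrent VTE, which is wider than Section 7.1 and conflicts with Section 6.3.4, so a few subjects may end with no assessable primary outcome

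*Combined protocol and SAP*

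**What the plan says.** Whether a subject has the Month 3 scan is governed by three places in the protocol.

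- **Table 17.1, footnote h** (on the VTE imaging row): "Optional Month 3 imaging can be done if recurrent VTE occurs prior to Month 3". Symptoms and adjudication are not mentioned.
- **Section 6.3.4**: "All randomized subjects including those that have discontinued treatment will have an EOT assessment at Month 3". The procedures for that visit include "Radiologic examination using the same diagnostic technique used at baseline to determine the thrombotic burden". There is no exception after a recurrence.
- **Section 7.1**: burden is compared between baseline and Month 3 "in the absence of symptomatic recurrent VTE". The exception covers symptomatic recurrence only.

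What counts as a primary event is set elsewhere.

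- **Recurrence component (Section 7.1)**: imaging confirmation is needed, "and at least one of the symptoms of VTE in the following table".
- **Burden component (Section 7.1)**: "A thrombotic burden endpoint will be registered if there is no regression of the thrombus size or extension of the thrombus at Month 3 visit". Cohort 5 has a 6-to-12-week equivalent.
- **Adjudication**: Section 6.2 says "All suspected VTE and bleeding endpoints as well as hepatic abnormalities identified by the Investigator will be adjudicated by the CEC". Section 3.3 bases the final analyses on adjudicated results.
- **No event (Section 11.4.1.1)**: the subject is censored at 3 months + 3 days or at the last complete outcome assessment, whichever is earlier. Section 11.2 says missing data are generally not imputed.

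**The concern.** The Month 3 scan appears to carry much of the primary endpoint. Section 7.5 cites rates of unchanged burden of 14.8%, 17% and 18%, against an expected composite rate of 28% in the control arm (Section 11.6). A rule that excuses the scan should therefore apply only to subjects who already have a countable event.

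Footnote h is not limited in that way. A site that follows the schedule can omit the scan after a recurrence that later turns out not to satisfy the recurrence component. The treatment is open label, and the footnote names no adjudication step before the scan is left out. Blinded adjudication cannot read an image that was never taken. The subjects concerned are also ones in whom a clot problem was at least suspected, so the missing assessments would not be a random sample.

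**Working it through.** **1. The plan's own figures.** Inputs from Section 11.6: margin 1.5, assumed hazard ratio 0.76, two-sided alpha 0.05, power 80%, 1:1 allocation. Schoenfeld's formula gives events = 4 × (1.960 + 0.842)² / [ln(1.5/0.76)]² = 31.4 / 0.462 = 68, with power 80.0%. With an edoxaban rate of 0.28 × 0.76 = 21.28%, the mean event rate is (28% + 21.28%)/2 = 24.64%, and 274 × 0.2464 = 67.5 events. The stated 68 events and 274 subjects are reproduced. No stated figure is wrong; the point is about wording.

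**2. Is the footnote wider than Section 7.1?** Section 7.1 lists imaging criteria for recurrent VTE that rest on imaging alone, and separately adds a symptom for symptomatic recurrent VTE. The term in footnote h can therefore be read to include an asymptomatic imaging finding.

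**3. Can such a finding arise before Month 3?** Yes, though not often by schedule. Section 6.3.3.2 allows imaging at Month 2 if needed. Section 6.3.1 provides a 6-week image in Cohort 5 when that duration is chosen.

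**4. What happens if the scan is then omitted?**

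| Case | Recurrence component | Burden component | Result |
|---|---|---|---|
| Symptomatic recurrence, accepted by the CEC | Met | Not needed | Event; omission is harmless for time to first event |
| Index clot extends on an early image, no listed symptom | Not met | Not registered at Month 3; use of the early image is unclear | May be censored |
| New clot elsewhere, no listed symptom | Not met | Index clot not assessed at Month 3 (Section 15.10 ties burden to the index VTE) | May be censored |
| Site suspects recurrence, CEC finds imaging does not confirm it | Not met | Index clot not assessed at Month 3 | May be censored, but no clot failure has been shown |

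**5. How many?** The documents give no rate of asymptomatic or unconfirmed recurrence. Take the 5.6% and 12.5% recurrence rates of the randomized pediatric trial in Section 1.1, and *assume* that 10% to 30% of recurrences are asymptomatic or not accepted and that every such scan is omitted:

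- low: 274 × 0.056 = 15.3; × 0.10 = 1.5 subjects
- high: 274 × 0.125 = 34.3; × 0.30 = 10.3 subjects

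These are subjects without a scan, not lost events.

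**6. Effect on power.** With N fixed, losing 2, 4 or 10 of 68 events lowers power from 80.0% to 78.9%, 77.6% or 73.5%. Replacing a lost event takes about 1/0.2464 = 4 more subjects.

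**7. Unequal loss, as illustration only.** Take 137 per arm, a control rate of 28% and a true hazard ratio of 1.5. Expected events are 38.4 on control and 137 × (1 − 0.72^1.5) = 53.3 on edoxaban. If 0, 2, 4 or 6 edoxaban events alone are lost, the apparent hazard ratio is 1.50, 1.43, 1.36 or 1.29. The chance of declaring non-inferiority is 2.5%, 4.2%, 6.8% or 10.4%. Loss from the control arm would push the other way.

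**The case against.** The strongest reply is that the body of the protocol already has the rule. Section 7.1 states the exception precisely, Section 6.3.4 requires the scan, and footnote h may be shorthand, since the protocol uses the term recurrent VTE loosely in several places. On that reading the waiver costs nothing, because the subject already has a first event. This is a fair reading, but the footnote does not say so, and a site working from the schedule could reasonably follow it as written.

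A second reply is that an early image need not be lost. Section 7.1 describes the composite as covering the first 3-month period, Section 11.4.1.1 counts events from randomization, and under Sections 6.2 and 15.10 the CEC receives the images and adjudicates thrombotic burden. A reader might infer that a proven clot failure is certain to go uncounted; the documents do not support that. Equally, the registration sentence in Section 7.1 points to the Month 3 visit, so they do not settle that an early extension would count.

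Third, the group is narrow. The symptom list is broad (pain, swelling, cough, fever and others), early imaging is mostly unscheduled, and the site must also choose to skip the scan. That stands, and it limits the size of the problem.

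**Conclusion.** The conflict between footnote h, Section 7.1 and Section 6.3.4 is real. It can leave a subject with an asymptomatic or unaccepted recurrence censored without an assessable primary outcome, unless the CEC counts an earlier image. The number is probably small. The range of about 2 to 10 subjects rests on an assumed 10% to 30% share and on every such scan being omitted.

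Three stronger readings should be resisted.

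- Dividing by the event target (1.5/68 = 2.3% to 10.3/68 = 15.1%) would suggest that up to 15% of events are lost. That treats every unscanned subject as a burden failure, and some would show regression at Month 3. A recurrence that the CEC rejects on imaging is not a proven failure at all.
- A reader might infer that the hazard ratio is biased in favour of edoxaban. Differential omission is possible in an open-label trial, but nothing in the documents shows it or its direction.
- A reader might infer that power is lost. Section 11.6 lets enrolment be adjusted to reach 68 events, so the more likely cost is some extra recruitment.

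This is an inconsistency worth correcting because the correction is cheap. It does not undermine the design.

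**What to change.** Reword only the Month 3 sentence of footnote h, to this effect: *the Month 3 image is mandatory for every subject, as in Section 6.3.4; it may be left out only when the CEC has confirmed, before Month 3, a symptomatic recurrent VTE that meets Section 7.1; while adjudication is pending, the scan is done.* The last clause matters because the documents give no adjudication turnaround time.

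In Section 7.1, state whether asymptomatic extension seen on an earlier scan counts as a burden event and, if so, what date it carries in the time-to-event analysis.

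Leave the Month 12/Discontinuation sentence of footnote h as it is. There, an image has already been taken for the recurrence, and the primary endpoint is not affected.

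The cost is two wording changes and a few Month 3 scans that Section 6.3.4 already requires. The design figures (68 events, 274 subjects, 80.0% power) do not change.

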17.2. Additional Information on Investigational Product Use in Pediatric Subjects

Recommendations per CHEST 2012 Guidelines²⁶

Table 17.2: Doses of LMWH (enoxaparin) used in Pediatric Subjects

Drug	Age	Initial Treatment Dose	Initial Prophylactic Dose
Age -dependent Dose of Enoxaparin	<2 months	1.5 mg/kg/dose q12h	0.75 mg/kg/dose q12h
	>2 months	1.0 mg/kg/dose q12h	0.5 mg/kg/dose q12h
Enoxaparin has 110 anti-factor Xa units/mg			

Table 17.3: Protocol for Anticoagulation Therapy to maintain an INR between 2.0 and 3.0 for Pediatric Subjects (Warfarin treatment)

1	Day 1: if the baseline INR is 1.0 to 1.3: Dose 0.2 mg/kg orally	
2	Loading 0.2 mg/kg Days 2-4: if the INR is:	
	INR	Action
	1.1 - 1.3	Repeat initial loading dose
	1.4 - 1.9	50% of initial loading dose
	2.0 - 3.0	50% of initial loading dose
	3.1 - 3.5	25% of initial loading dose
	>3.5	Hold until INR \leq 3.5; then restart at 50% decreased dose
3	Maintenance oral anticoagulation dose guidelines:	
	INR	Action
	1.1 - 1.4	Increase by 20% of dose
	1.5 - 1.9	Increase by 10% of dose
	2.0 - 3.0	No change
	3.1 - 3.5	Decrease by 10% of dose
	>3.5	Hold until INR \leq 3.5; then restart at 20% decreased dose

INR = international normalized ratio

Table 17.4: Doses of Fondaparinux

Fondaparinux Doses	Target Therapeutic Fondaparinux Level
0.1 mg/kg, once a day	0.5-1 mg/L (blood drawn at 3 hours post-dose)
0.05 mg/kg/day (for subjects with renal disease).	
Dose Adjustment of Fondaparinux	
Fondaparinux Level (mg/L)	Doses Adjustment
<0.3	Increase dose by 0.03 mg/kg
0.3 - 0.5	Increase dose by 0.01 mg/kg
0.5 - 1	No change
1 - 1.2	Decrease dose by 0.01 mg/kg
>1.2	Decrease dose by 0.03 mg/kg

17.3. Effective Methods of Birth Control

Women of childbearing age are defined as those women capable of conceiving, being pregnant with, and giving birth to children, and are eligible for the study based on the inclusion and exclusion criteria.

Female subjects of childbearing potential must test negative for pregnancy at Screening with a highly sensitive test and must consent to avoid becoming pregnant by using an approved contraception method throughout the study.

The following use of reliable method(s) of contraception, and/or abstinence, for the duration of therapeutic product exposure is recommended:

Highly effective methods of contraception, when used consistently and correctly, result in low failure rates. These may include:

- Combined (estrogen and progesterone-containing) hormonal contraception associated with inhibition of ovulation
 - Oral
 - Intravaginal
 - Transdermal
- Progesterone-only hormonal contraception associated with inhibition of ovulation
 - Oral
 - Injectable
 - Implantable
- Intrauterine Device (IUD)
- Intrauterine Hormonal-Releasing System

- Bilateral Tubal Occlusion
- Vasectomized partner
- Sexual Abstinence

Effective methods may include:

- Barrier methods of contraception (eg, male condom, female condom, cervical cap, diaphragm, contraceptive sponge).

Note: When used consistently and correctly, “double barrier” methods of contraception (eg, male condom with diaphragm, male condom with cervical cap) can be used as an effective alternative to the highly effective contraception methods described above.

Oral contraception is not contraindicated with edoxaban but maybe not recommended in patients with high risk of thromboembolic events. The use of oral contraception is per investigator’s discretion.

17.4. Prohibited Concomitant Medications

The list here (in the protocol) is static and reflects the list at the time of the current version of the protocol. If there are changes to this list during the study, the changes will not be considered a protocol amendment and the list in this appendix will not be updated unless the protocol is being amended for other reasons as well.

Subjects on these drugs at the time of planned randomization will be excluded from the study. After randomization, use of these drugs will require a study drug permanent discontinuation unless advised otherwise in the sections below. The Investigator is encouraged to contact the Medical Monitor for further guidance.

Sites will receive a contact card where the following numbers (24-hour Urgent Medical Contact) are provided:

PPD [REDACTED] (primary number)
PPD [REDACTED] (alternative number)

17.4.1. Antiplatelet Drugs

Use of any antiplatelet medication as single or dual agent antiplatelet therapy is prohibited while on study drug except for low dose aspirin defined as 1-5 mg/kg/day with maximum of 100 mg/day. If there is a clinical indication for single or dual agent antiplatelet therapy, the subject will need to be discontinued from the study treatment.

Examples of non-aspirin oral antiplatelet agents include the following:

- Thienopyridienes: clopidogrel (Plavix®), ticlopidine (Ticlid®), prasugrel (Effient®)
- Dipyridamole: Persantine®, Aggrenox®
- Cilostazol (Pletal®)
- Pentoxifylline (Trental®)

- Sulfopyrazone (Anturane®)
- Ticagrelor (Brillanta®)

IV antiplatelet agents include the following:

- Glycoprotein IIb/IIIa inhibitors: Abciximab (ReoPro™), Eptifibatide (Integrilin®),
- Tirofiban (Aggrastat®)
- PGY12 Inhibitor: Cangrelor
- Dextran

17.4.2. Oral Anticoagulants Other than Study Drug

Oral anticoagulants including Factor IIa inhibitors (eg, dabigatran), and FXa inhibitors (eg, rivaroxaban, apixaban) are prohibited in both treatment arms. The only allowed oral anticoagulants are the study drugs.

17.4.3. Parenteral Anticoagulants

Parenteral anticoagulants are prohibited in the edoxaban treatment arm. Direct thrombin inhibitors are prohibited in edoxaban arm and in the SOC arm.

Examples of prohibited parenteral anticoagulant medications include the following:

- Low molecular weight heparins: enoxaparin (Lovenox®, Clexane®), dalteparin (Fragmin®), tinzaparin (Innohep®, Logiparin®), reviparin (Clivarin®), nadroparin (Fraxiparine®), ardeparin (Normiflo®), certoparin (Sandoparin®), parnaparin (Fluxum®)
- Direct thrombin inhibitors: bivalirudin (Angiomax®), argatroban, (Acova®), desirudin (Iprivask®), lepirudin (Refludan®)
- FXa inhibitors: fondaparinux (Arixtra®)

